### 5.6.2 Specimen Shipping Instructions

Tissue in formalin must be shipped on the day of collection. Collect and ship on Monday through Wednesday.

Archival (FFPE) tissue may be shipped on Monday through Thursday.

Fresh blood may be shipped on Monday through Friday. Please select “Saturday Delivery” when shipping fresh blood on a Friday.

#### 5.6.2.1 Shipping of FFPE Blocks and Glass Slides

1. Before packaging blocks or slides, verify that each specimen is labeled according to Section 5.4.2.2.
2. Blocks should be placed in a hard-sided container, preferably a special block holder, to protect the specimen. Glass slides are to be placed in plastic slide holders. Place tissue paper on top of the separated slides prior to closing the slide holder to reduce slide movement during shipment.
3. Place the blocks or slides in a reinforced cardboard shipping box with appropriate packaging filler to minimize movement of specimens within the shipping box.
4. Include a copy of the forms listed above and a shipping manifest from the Specimen Tracking System with each shipment.

5. Please include a cold pack when shipping on hot days and extra insulation on cold days.
6. Ship specimens to the address listed below. FedEx Priority Overnight is strongly recommended to prevent delays in package receipt.

#### 5.6.2.2 Shipping Blood in an Ambient Shipper

1. Before packaging specimens, verify that each specimen is labeled according to the instructions in Section 5.4.2.1 and that the lids of all primary receptacles containing liquid are tightly sealed.
2. Prepare the SAF-T-TEMP Gel Pak for shipment. **Note:** If contents of the Pak are crunchy, place Pak in a warm water bath until gel is smooth. **Do not refrigerate, freeze, or microwave.**
3. Place the SAF-T-TEMP Pak in bottom of insulated chest. **Note:** The insulated chest must be shipped inside the provided cardboard box(es).
4. Place the blood collection tubes in zip-lock bags.
5. Next, place blood into a biohazard envelope with absorbent material. Expel as much air as possible and seal the envelope securely.
6. Place the biohazard envelope into a Tyvek envelope. Expel as much air as possible and seal securely.
7. Place packaged blood collection tube(s) and a copy of the shipping manifest from the Sample Tracking System on top of SAF-T-TEMP Pak.
8. Place the lid on the insulated chest.
9. Close the outer flaps of the shipping box and tape shut.
10. Attach a shipping label to the top of the shipping container.
11. Attach an Exempt Human Specimen sticker to the side of the box.
12. Ship specimens via overnight courier to the address below. FedEx Priority Overnight is strongly recommended to prevent delays in package receipt.

#### 5.6.2.3 Shipping Ambient Tissue in a Single-Chamber Kit

1. Before packaging specimens, verify that each specimen is labeled according to the instructions in Section 5.4.2 and that the lids of all primary receptacles containing liquid are tightly sealed. The lids of formalin jars should be wrapped in parafilm. Absorbent material must be placed around each primary container that holds liquid.
2. Place the specimens in zip-lock bags. Use a separate bag for each specimen type.
3. Place specimens into the secondary pressure vessel surrounded by bubble wrap. Place the lid on the secondary pressure vessel and set it inside the kit chamber.
4. Place a copy of the shipping manifest and corresponding reports such as pathology, surgical, or radiology reports into the insulated shipping container.
5. Set the lid on top of the container. Close the outer flaps and tape shut.
6. Attach a shipping label to the top of the shipping container.
7. Attach an Exempt Human Specimen sticker to the side of the container.
8. Ship specimens via overnight courier to the address below. FedEx Priority Overnight is strongly recommended to prevent delays in package receipt.

NCI Protocol #: 10399  
Version Date: August 17, 2021

## 5.7 Shipping of Specimens from Clinical Site to Other Laboratories

### 5.7.1 Shipping of Specimens to [name] laboratory (MITS core)

#### 5.7.1.1 Specimen Shipping Instructions

##### PBMC

- PBMC isolated as described in section 5.5.3.2.1 should be shipped on dry ice, priority overnight for next day morning delivery
- PBMC should be shipped on Monday-Wednesday and **should not** be sent on Thursdays or Fridays.
- Sites shipping samples should give the UVA MITS Core 24 business hours of notice prior to shipping to ensure that staff will be available to receive the package. If Monday shipping is planned, please notify during business hours on Friday.

Email: [[contact]](mailto:[contact]) (**notify immediately of anticipated shipment**)

#### 5.7.2 Shipping of Blood Samples to JHU APC

##### 5.7.2.1 Specimen Shipping

- Specimens should be stored through the end of Cycle 2 and shipped as a batch by participant (more than one participant/shipment is acceptable).
- A participant's samples should be shipped to the JHU APC lab within 2 weeks of the last sample's collection date. (i.e., if C2D2 sample is collected on 9/1/2021, all of that participant's samples should be at the JHU APC lab by 9/15/2021).
- The JHU APC lab may contact the study team to request shipment off-schedule.
- **Please ship only 1 aliquot to the JHU APC laboratory within each shipment. Once receipt is confirmed, the back-up aliquot(s) may also be shipped. The back-up aliquots can be shipped at a later date with subsequent batches of samples for other participants.**

###### 5.7.2.1.1 Preparing the Specimen Shipment

- Samples should be stored in cardboard boxes (5 1/8" x 5 1/8" x 2", LxWxH) with dividers. (e.g., VWR Box item number is 82021-114; divider item number is 82007-154.)
- Please organize the samples by Patient and Time point in the box.
- Do not store in plastic bags (they break on dry ice and labels will detach).
- A copy of each of the pharmacokinetic sample collection forms for the respective patients or a sample list should be included with each shipment. To prevent problems with illegible writing on tubes, consider numbering them (in addition to sample label) and numbering samples on the sample sheet.
- Note the study number, PI, and the drugs used/to be measured (i.e. entinostat).

- A name, phone number and email address should be included with samples so that receipt can be acknowledged.
- Please notify the lab by email ([[contact]](mailto:[contact])) or [contact] or [contact]) at least 24 hours prior to shipment.

#### 5.7.2.1.2 Specimen Shipping Instructions

- Samples collected at Johns Hopkins University can be transferred utilizing the current SOPs.
- All samples should be shipped via overnight express courier in insulated containers with enough dry ice to maintain the samples in a frozen state.
- Overnight shipments should occur on Monday through Wednesday except when the following day is a holiday.
- Please notify the lab by email ([[contact]](mailto:[contact])) or [contact] or [contact]) at least 24 hours prior to shipment.

#### 5.7.3 Shipping of Blood Samples to OSUCCC PhASR

##### 5.7.3.1 Specimen Shipping

- Specimens should be stored through the end of Cycle 8 and shipped as a batch by participant (more than one participant/shipment is acceptable).
- A participant's samples should be shipped to the OSUCCC PhASR lab within 2 weeks of the last sample's collection date. (i.e., if C8D1 sample is collected on 9/1/2021, all of that participant's samples should be at the OSUCCC PhASR lab by 9/15/2021).
- The OSUCCC PhASR lab may contact the study team to request shipment off-schedule.
- **Please ship only 1 aliquot to the OSUCCC PhASR laboratory within each shipment. Once receipt is confirmed, the back-up aliquot(s) may also be shipped. The back-up aliquots can be shipped at a later date with subsequent batches of samples for other participants.**

##### 5.7.3.1.1 Preparing the Specimen Shipment

- Samples should be stored in cardboard boxes (5 1/8" x 5 1/8" x 2", LxWxH) with dividers. (e.g., VWR Box item number is 82021-114; divider item number is 82007-154.)
- Please organize the samples by Patient and Time point in the box.
- Do not store in plastic bags (they break on dry-ice and labels will detach).
- A copy of each of the pharmacokinetic sample collection forms for the respective patients or a sample list should be included with each shipment. To prevent problems with illegible writing on tubes, consider numbering them (in addition to sample label) and numbering samples on the sample sheet.
- Note the study number, PI, and the drugs used/to be measured (i.e. atezolizumab).
- A name, phone number and email address should be included with samples so that receipt can be acknowledged.

#### 5.7.3.1.2 Specimen Shipping Instructions

- All samples should be shipped via overnight express courier in insulated containers with enough dry ice to maintain the samples in a frozen state.
- Overnight shipments should occur on Monday through Wednesday except when the following day is a holiday.
- Please notify the OSUCCC PhASR lab by email ([[contact]](mailto:[contact])) within 24 hours prior to shipment.

### 5.8 Biomarker Plan

NCI Protocol #: 10399  
 Version Date: August 17, 2021

### List of Biomarker Assays in Order of Priority

Priority	Biomarker Name	Assay (CLIA: Y/N)	Use in the Trial and Purpose	Specimens Tested	Collection Time Points	Mandatory or Optional	Assay Laboratory and Lab PI
Tissue-based Biomarkers							
1	Whole Exome Sequencing (WES)	NGS CLIA: N	Integrated To identify genomic alterations and determine if they could be useful biomarkers for SCLC. Of specific interest are CREBBP and EP300 genes and TMB analysis.	DNA from FFPE Tumor	Archival or Baseline Disease Progression	M (archival or baseline) O (disease progression)	NCLN Genomics Laboratory [name]. [contact]
2	RNA Sequencing (RNAseq)	NGS CLIA: N	Exploratory To identify the transcriptional characteristics of response to treatment	RNA from FFPE Tumor	Archival or Baseline Disease Progression	M (archival or baseline) O (disease progression)	NCLN Genomics Laboratory [name]. [contact]
3	Transcriptional Regulators	Multiplex IHC CLIA: N	Exploratory To characterize the subtype of small cell lung cancer based on transcriptional regulators: ASCL1, NeuroD1, YAP2, POU2F3	Unstained slides from FFPE Tumor	Archival or Baseline	M	[name] Laboratory, Memorial-Sloan Kettering Cancer Center [name]., Ph.D. [contact]

NCI Protocol #: 10399

Version Date: August 17, 2021

Priority	Biomarker Name	Assay (CLIA: Y/N)	Use in the Trial and Purpose	Specimens Tested	Collection Time Points	Mandatory or Optional	Assay Laboratory and Lab PI
4	Immune Cell Markers	Multispectral IHC (Vectra) CLIA: N	Exploratory  To characterize the tumor microenvironment for PDL1, CD8, NK cells, regulatory and effector T-cells, arginase, and IDO.	Unstained slides from FFPE Tumor	Archival or Baseline  Disease Progression	M (archival or baseline)  O (disease progression)	[name] Laboratory, University of Virginia  [name].  [contact]
Blood-based Biomarkers							
1	Whole Exome Sequencing (WES)	NGS CLIA: N	Integrated Germline Control	DNA from blood in cfDNA Streck tubes	C1D1  Collected as part of specimen for ctDNA biomarker	M	NCLN Genomics Laboratory  [name].  [contact]
2	ctDNA	NGS CLIA: N	Exploratory  To identify genomic alterations in genes of interest, CREBBP and EP300, that may not be detectable in tissue. Identify possible mechanisms of resistance at time of progression	Plasma from cfDNA Streck tubes	C1D1  Disease Progression	M	NCLN Genomics Laboratory  [name].  [contact]

NCI Protocol #: 10399

Version Date: August 17, 2021

Priority	Biomarker Name	Assay (CLIA: Y/N)	Use in the Trial and Purpose	Specimens Tested	Collection Time Points	Mandatory or Optional	Assay Laboratory and Lab PI
3	Circulating Immune Cells	Flow Cytometry CLIA: N	Exploratory  To characterize circulating immune cells in response to treatment	PBMCs from Sodium Heparin Tubes	C1D1 C2D1 C3D1 C4D1 Disease Progression	M	[name] Laboratory, University of Virginia  [name].  [contact]
4	Immunogenicity	ELISpot CLIA: Y	Exploratory  To determine immunogenicity of treatment over time	PBMCs from Sodium Heparin Tubes	C1D1 C2D1 C3D1 C4D1 Disease Progression	M	[name] Laboratory, University of Virginia  [name].  [contact]
5	Entinostat Exposure	LC-MS/MS CLIA: N GLP: Y	Integrated Pharmacokinetic profile of entinostat	Plasma from Sodium Heparin Tubes	C1D1 pre-dose and approximately 0.5 and 2 hours after entinostat administration; C1 D2: prior to etoposide infusion; C1D8 pre-dose, C1D15 pre-dose; C2D1 pre-dose and approximately 0.5 and 2 hours after entinostat administration; C2 D2: prior to etoposide infusion	M	Johns Hopkins University Analytical Pharmacology Core  [name]., Ph.D.  [contact]

NCI Protocol #: 10399

Version Date: August 17, 2021

Priority	Biomarker Name	Assay (CLIA: Y/N)	Use in the Trial and Purpose	Specimens Tested	Collection Time Points	Mandatory or Optional	Assay Laboratory and Lab PI
6	Atezolizumab	ELISA CLIA: N GLP: Y	Integrated Pharmacokinetic profile of atezolizumab	Serum from Red top Tubes	C1D1 pre-dose and after the end of the atezolizumab infusion at the same time as the ~2 hours post entinostat PK; C2D1 pre-dose and after the end of the atezolizumab infusion at the same time as the ~2 hours post entinostat PK; C3D1 pre-dose and approximately 0.5 hours after the end of atezolizumab administration; C4D1 pre-dose and approximately 0.5 hours after the end of atezolizumab administration; C6D1 pre-dose and approximately 0.5 hours after the end of atezolizumab administration; C8D1 pre-dose and approximately 0.5 hours after the end of atezolizumab administration;	M	Pharmacoanalytical Shared Resource (PhASR), Ohio State University Comprehensive Cancer Center  [name].  [contact]

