
For archival tissue, a copy of the corresponding anatomic pathology report, labeled with the patient study ID and Universal ID, must be sent with the tissue and uploaded to Rave. If submitting slides, then slides must be processed in order, and numbered sequentially.
 
 For new biopsies, a fine needle aspirate (FNA) should be obtained for diagnostic purposes and submitted to pathology. Cores should be obtained for research and not submitted to pathology for review. The Tissue Biopsy Verification Form (Appendix E), a copy of the radiology and/or operative reports from the tissue removal procedure and the diagnostic anatomic pathology report must be sent with the tissue to the EET Biobank. All reports must be labeled with the patient study ID and Universal ID.
 
 For any PK sample, the PK samples are on the days of drug administration. If drug administration is shifted due to a holiday or inclement weather, the PK should be collected on that day (and not the exact day listed above).
 
 If etoposide is held for any reason, the accompanying entinostat PK sample should not be collected.
		

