Thrombocytopenia	Management/Next Dose for Entinostat
≤ Grade 1	No change in dose
Grade 2	Hold* until ≤ Grade 1. Resume at same dose level.
Grade 3	Hold until ≤ Grade 1. Resume at one dose level lower
Grade 4	Discontinue entinostat
* For grade 2 thrombocytopenia events occurring mid-cycle, treatment does not need to be held For thrombocytopenia events occurring between days 2 and 21 of each cycle, dose reductions at next cycle Day 1 may be made at investigator discretion, unless required as above	

Other non-hematologic AEs	Management/Next Dose for Entinostat
≤ Grade 2	No change in dose
Grade 3	Hold until ≤ grade 1. Resume at one dose level lower.
Grade 4	Discontinue entinostat

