### 9.3 Analysis of Secondary Endpoints

Adverse events and DLTs will be summarized by frequency and magnitude. The rate of feasibility of administering entinostat concomitantly with atezolizumab, carboplatin, and etoposide as determined by the proportion of participants who receive 3 or more cycles of the combination, will be calculated with a 90% confidence interval. The Kaplan Meier estimator will be used to estimate survival curves for all time to event endpoints including progression free survival (PFS) and overall survival (OS). The 9 month PFS rate will be estimated with a 90% confidence interval. Anti-tumor endpoints, including measures of tumor response and symptom relief, will be summarized using descriptive statistics. Tumor response will be measured using RESIST 1.1 criteria and reported as overall response rate (ORR) with a 95% confidence interval. Entinostat exposure will be determined for each patient using mixed effects pharmacokinetic modeling. Atezolizumab clearance, including a time-varying rate of change, will be determined for each patient using mixed effects pharmacokinetic modeling. Exposure-response assessments will be assess associations between entinostat exposure with the clinically significant toxicity, PFS and OS. Clearance-response will be assessed between baseline or time-varying atezolizumab clearance with the presence of cachexia, PFS and OS. Biomarker evaluations from exploratory objectives will be summarized using descriptive statistics.

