
e: Tumor measurements are repeated every 6 weeks (+/- 1 week) for year 1.
 
f: Tumor measurements are repeated every 3 months (+/- 2 weeks) for year 2, then every 6 months (+/- 1 month) thereafter. Documentation (radiologic) must be provided for patients removed from study for progressive disease.
 
g: CT Chest/Abd/Pelvis are performed within 4 weeks of study registration and then every 6 weeks(+/- 1 week) for year 1, every 3 months (+/- 2 weeks) for year 2, then every 6 months (+/- 1 month) thereafter until progression. Patients who discontinue study treatment for reasons other than disease progression will continue radiographic evaluations per this schedule during Follow-Up until disease progression is documented. For pts with untreated brain mets, brain MRI is performed within 4 weeks of study enrollment and then subsequently at same schedule as CT imaging; otherwise as clinically indicated.
 
h: If participant is no longer coming to the study site, study staff will call or email the participant to check overall survival every 3 months for years 1-2, then every 6 months (+/- 1 month) until 5 years from registration.
 
i: Day 1 of every even cycle.
 
j: May continue per investigator/patient discretion as standard of care. Labs, vitals, performance status should be done as routine standard of care and are not indicated on this table. End of treatment visit may occur on a day when standard of care atezolizumab is administered or a separate day.
 
k: Tumor biopsy (optional), blood collection in cfDNA Streck tube for ctDNA, Flow cytometry, and ELispot are to be performed at the time of progression. Refer to Sections 5.1 and 5.5.
 
l: Entinostat PK on Cycles 1-2, Day 1: prior to entinostat, ~0.5 hr post dose, and ~2 hrs post dose; Cycles 1-2, Day 2: prior to etoposide infusion; Cycle 1, Day 8 and 15: prior to entinostat.
 
m: Atezolizumab PK on Day 1 of Cycles 1 and 2: prior to atezolizumab and after the end of the atezolizumab infusion at the same time as the ~2 hr post entinostat PK. On Day 1 of Cycles 3, 4, 6, and 8: prior to atezolizumab and ~0.5 hr after completion of atezolizumab infusion.
 
n: Free or total T3/T4 may be performed per institutional standards.
										

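### Entinostat PK draws are tied to dosing days and no rule covers a toxicity hold, so patients held from Cycle 1 Day 8 who never resume may keep only first-24-hour samples, which can distort the exposure-toxicity analysis

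*Combined protocol and SAP*

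**What the plan says.** Sections 5.1 and 5.8 schedule ten entinostat samples: three on C1D1, one each on C1D2, C1D8 and C1D15, three on C2D1 and one on C2D2. The first-dose samples are "C1D1 pre-dose and approximately 0.5 and 2 hours after entinostat administration". The other Cycle 1 times are "C1 D2: prior to etoposide infusion; C1D8 pre-dose, C1D15 pre-dose", and Study Calendar footnote l gives "Cycle 1, Day 8 and 15: prior to entinostat".

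Two footnotes to the Section 5.1 table govern what happens when dosing departs from schedule:

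- Footnote 4, attached only to C1D2 and C2D2: "If etoposide is held for any reason, the accompanying entinostat PK sample should not be collected".
- Footnote 3: "For any PK sample, the PK samples are on the days of drug administration". It then adds: "If drug administration is shifted due to a holiday or inclement weather, the PK should be collected on that day". A dose held for toxicity is not mentioned.

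Section 7.2.3 holds entinostat for toxicity. For Grade 3 thrombocytopenia, for instance, the instruction is "Hold until ≤ Grade 1. Resume at one dose level lower". Section 9.3 estimates each patient's exposure with a mixed-effects PK model and will assess "associations between entinostat exposure with the clinically significant toxicity, PFS and OS". It defines neither the exposure measure nor its time window, and it does not say how samples missing because of toxicity will be handled.

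**The concern.** Footnote 4 drops a Day 2 sample although entinostat was already taken on Day 1, so a level at that time would be valid. The larger issue is Days 8 and 15. If a sample is defined as preceding a dose, and PK belongs on dosing days, a site that holds the dose has no instruction to draw.

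The missingness is then tied to the outcome. Under Section 6.2, receiving none or one of the three Cycle 1 entinostat doses because of treatment-related events, when related to entinostat, is itself a DLT. A patient held on both Day 8 and Day 15 for that reason is therefore a DLT patient by definition, and is the one whose later samples are at risk. Cycle 2 samples follow only if dosing resumes. Under 7.2.3 it does not resume after Grade 4 thrombocytopenia or Grade 4 non-hematologic events. At Level 1, where a reduction is required, the first step in 7.2.1 is discontinuation.

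At stake is objective 1.3.5. Few DLT patients are expected, and a sample not drawn cannot be recovered at analysis.

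**Working it through.** The plan states no precision or power for this analysis, so there is no figure to reproduce.

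**Step 1. Count the samples.** Footnote 4 reaches 2 of 10. If a hold from Day 8 also removes sampling and dosing never resumes, the losses are C1D8, C1D15, three at C2D1 and one at C2D2: 6 of 10. Four remain. One of these precedes any drug, which leaves three concentrations at about 0.5, 2 and 24 h.

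**Step 2. What 24 hours can show.** Section 2.2.1.4 gives a half-life range of 54 to 161 h and a fasted median of 140 h. The fractional decline is 1 − 2^(−t/half-life).

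| Half-life | Over 24 h | Over 168 h |
|---|---|---|
| 54 h | 1 − 2^(−0.444) = 27% | 1 − 2^(−3.111) = 88% |
| 140 h | 1 − 2^(−0.171) = 11% | 1 − 2^(−1.2) = 56% |
| 161 h | 1 − 2^(−0.149) = 10% | 1 − 2^(−1.043) = 51% |

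At 140 h, the 24 h decline is smaller than an assumed residual error of 20% on one measurement. The Day 8 decline is well above it.

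**Step 3. Correlation of estimated with true clearance (CL).** These are simulations of a one-compartment oral model. Assumptions not in the documents, for the independent case: absorption rate 1/h, about 50% CV on CL, 40% on volume (V), 20% residual error. Variants let CL and V move together. Results at 140 h:

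| CL and V | 0.5, 2 and 24 h only | Day 8 and 15 draws kept, doses held |
|---|---|---|
| Independent | 0.26 to 0.35 | 0.95 to 0.97 |
| Correlated, e.g. through bioavailability | 0.51 to 0.80 | 0.96 to 0.98 |

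Full sampling gives 0.96 to 0.97. Dropping only the Day 2 samples gives 0.96 against 0.97. If all patients resume at C2D1, the correlation is 0.98. In the independent case, the early-only value is 0.61 at 54 h and 0.23 at 161 h.

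**Step 4. Effect on the toxicity contrast.** This is a separate simulation with 1,200 patients per setting. Assumptions: SD 0.4 on log CL and 0.5 on log V (independent), residual SD 0.25, toxicity about 25%, log-odds slope 0.7 per SD of log exposure. Entries are mean log exposure with toxicity minus without. Samples are removed only in patients with toxicity.

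| Samples available | 54 h | 140 h | 161 h |
|---|---|---|---|
| True difference | 0.259 | 0.231 | 0.203 |
| All ten | 0.237 | 0.190 | 0.150 |
| Day 2 samples lost | 0.230 | 0.191 | 0.141 |
| All after C1D8 lost | 0.188 | 0.114 | 0.061 |
| All from C1D8 on lost | 0.049 | 0.061 | 0.030 |

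Relative to all ten samples, losing everything from C1D8 removes 1 − 0.049/0.237 = 79%, 1 − 0.061/0.190 = 68% and 1 − 0.030/0.150 = 80%. The Monte Carlo standard error of the true difference is about 0.4 × √(1/300 + 1/900) = 0.027. The rows share the same patients, so comparisons down a column are steadier than that. With no true association, every sampling row lies between about −0.02 and 0.03.

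**Step 5. The exposure measure.** Suppose exposure means the cumulative amount received in Cycle 1 and patients with toxicity get 1 of 3 doses. The log difference then shifts by ln(1/3) = −1.10. At 140 h, 0.231 − 1.099 = −0.868. Across half-lives the result is −0.84 to −0.90 under a true positive association and −1.05 to −1.08 under none.

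**The case against.** The strongest reply is that the only written cancellation rule is footnote 4, and it does almost no harm. That stands. A reader might infer that the protocol cancels entinostat samples whenever entinostat is held, but no passage says so. Footnote 3 addresses holidays and weather. The calendar marks Day 8 and Day 15 without condition, and 5.1 and 5.8 call the samples mandatory. Section 6.1.1 allows entinostat at any time on those days, so a site could draw with the blood count before deciding to hold. What remains is an ambiguity that sites could resolve differently.

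Second, the severe loss needs a hold from Day 8 and no resumption. Section 7.2.3 requires no hold for mid-cycle Grade 2 cytopenias and lets many others resume. Delayed Day 1 treatment would carry its samples with it. Toxicity after Day 8 leaves that sample in place; early samples plus Day 8 gave a correlation of 0.86. This also stands.

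Third, independent variation in CL and V implies a 95% half-life range of about 43 to 460 h, wider than the documented 54 to 161 h, and Section 2.2.1.4 reports considerable variation in absorption. Early samples may therefore be more informative than 0.3 suggests. They also recover first-dose AUC over 0 to 24 h well (correlation 0.95). This is why a range is given. It does not remove the gain from keeping the draws, which gave at least 0.95 in every 140 h setting.

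**Conclusion.** The gap is real but narrow. It affects patients held from Day 8 who do not resume, if sites read the footnotes in the natural way. For them, the correlation with true clearance at 140 h falls from about 0.96 to between about 0.3 and 0.8, depending on how CL and V vary together. Every simulated figure rests on assumptions the documents do not supply.

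A reader might conclude that the planned analysis is biased toward no association by a known amount. The documents do not support that. For a clearance-based or dose-normalized measure, a true association shrinks. For cumulative exposure received, the bias can run toward a false inverse association, and 9.3 does not say which is meant. A simulation with 24 patients, all those with toxicity held on both days and none resuming, recovers 35% of the true difference, rising to 65% if half resume. That is a corner case, not a forecast.

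Objective 1.3.5 is exploratory, and the MTD decision does not use these data. The change is worth making because it is cheap and cannot be made retrospectively.

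**What to change.** - In 5.1 (footnotes 3 and 4), 5.8 and calendar footnote l, state that the C1D8, C1D15 and C2D1 pre-dose-time entinostat samples are drawn at the scheduled visit whether or not entinostat is given that day. The C2D1 post-dose samples continue to follow the dose.
- Collect the Day 2 sample whenever the patient is on site, whether or not etoposide is given.
- Record the actual sample time and the time of the last entinostat dose taken.
- In 9.3, name an exposure measure and window that toxicity-driven holds do not themselves alter, for example model-based clearance or dose-normalized AUC.

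The cost is one 4 mL tube at visits that already include a blood count and chemistry, plus wording changes. Some Day 2 samples will still be missed when the patient does not attend. No dose or hold rule changes.
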